#### **Infectious Complication**

- CLABSI (Central Line Associated Bloodstream Infection)
- Exit Site Infection

#### **Thrombotic Complication**

- Thrombotic occlusion
- Catheter patency rate
- Drug precipitates

## **CASCADE STUDY**

## **Catheter Dwell – Appendix B**

- Line insertion date
- Line insertion time
- Line removal date
- Line removal time
- Discharge Order Time for catheter removal
- Line Removal time from discharge order

## **STUDY DESIGN**

This is a single site retrospective (non-experimental) study utilizing the electronic medical record, both descriptive and correlational methods.

## **METHODOLOGY**

Clinician adherence to hospital approved EBP guidelines, policies, and procedures will be obtained by way of a retrospective medical record review to include data abstraction from nursing and physician notes, consultation, admission notes, discharge notes, medical history, laboratory and diagnostic tests, flow sheets, and other relevant clinical documentation. EPIC, the electronic medical record will be the primary source for the retrospective data collection. The hospital approved EBP guidelines, policies and procedures to evaluated clinican variation in the care and management of CVCs, PICCs and HD catheters in the Department of Patient Care (DOPC) and Infection Control (IC) are listed below and summarized in Appendix A.

1. DOPC Clinical Procedures – Apheresis Catheter Maintenance – A-2
2. DOPC Clinical Procedures Central Venous Catheter Maintenance and Removal – C-10A

3. DOPC Clinical Procedures – Adult Dialysis Catheter ( Care and Use) D-2
4. DOPC Clinical Procedures – Implantd Venous Acess Devices Maintenance – I-1
5. DOPC Clinical Procedures – PICC (Peripherally Inserted Central Catheters) Maintenance – P-8
6. DOPC Dialysis – Initiation of Dialysis via Central Venous Catheter – R-98
7. IC- Equipment, Supplies – Insertion and Maintenance of Central Cannulas in Large Vessels – 706-2-1
8. IC- Equipment, Supplies – Insertion and Maintenance of Central Venous Catheters for Parenteral Nutrition – 706-8

This method is based on the 1991 seminal work by Brennan et al., considered to be the gold standard of epidemiological analysis to identify variation in clinical practice, specifically related to treatment plans, morbidity, mortality and cost. (Cassidity, Marsh, Holleran, & Ruhll, 2002; Murray et al).

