## **PRIMARY ENDPOINTS**

1. To document number of mechanical/technical, thrombotic, and other adverse outcomes associated with CVCs, PICCs and HD catheters in two groups:
  - 1a. Clinicians interventions and management in adherence with hospital approved EBP guidelines for CVCs, PICCs and HD catheters.
  - 1b. Clinicians interventions and management not in adherence with hospital approved EBP guidelines for CVCs, PICCs and HD catheters.

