#### Catheter Management and Care Documented: Appendix

Number and rate of times that the following best practice indicators were documented

- Department/Unit of catheter insertion
  - Operating Room
  - Bed-side
    - Cardiac Intensive Care Unit (CICU), Surgical Intensive Care Unit (SICU), Medical Intensive Care Unit (MICU)
  - Interventional Radiology
- Personnel performing the insertion
- Physician assistance Advance Practice Nurse

- Catheter insertion site
  - Subclavian
  - Internal jugular
  - Femoral
  - Cephalic vein
  - Basilic vein
  - Brachial vein
- Frequency of dressing changes
- Mask was used during dressing change procedure
- Mask was used during access procedure for CVCs, PICCs, HD catheters
- Accessing central line procedure
- Scrub the hub procedure document
- Alcohol impregnated cap
- CUROS cap
- Frequency of line flushing
- Flush with normal saline as per post infusion policy
- Flush with heparin lock as per post infusion policy
- Syringe size used for flushing documented
- Infusion pump high pressure alarm documented
- Type of products infused through line (medications, etc)

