## **DATA MANAGEMENT**

All data in this study will be obtained from multiple sources: EPIC and the Business Intelligence Department and review of clinician notes. REDCap will be utilized to for study data entry. All study data will be exported to Microsoft Excel for data analysis preparation, and imported for SAS version 9.4 (SAS Institute Inc. Cary, NC, USA) for data analysis.

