
## Appendix C

### CASCADE STUDY DATA COLLECTION TOOL

| Please provide in this format: |            |             |     | Not in this format: |            |                          |     |
|--------------------------------|------------|-------------|-----|---------------------|------------|--------------------------|-----|
| MRN                            | HAR        | Medication  | ... | MRN                 | HAR        | Medication               | ... |
| 1234567                        | 2000000001 | Albuterol   | ... | 1234567             | 2000000001 | Albuterol
Simvastatin | ..  |
| 1234567                        | 2000000001 | Simvastatin | ... |                     |            |                          |     |

| Item  | Values/examples   | Description  |
|---|---|--|
| MRN   | 7 or 9 digit number   | Patient's MRN  |
| HAR   | 10 digit number   | Patient's HAR  |
| Name  | XXX, XXX alphanumeric   | Patient full name  |
| Sex   | Male/Female   | Patient's gender   |
| Age   | Number  | Patient's age at admission (number)  |
| Line, Drain, Airway, Tubes and Wound (LDAW) of the following types: CVC, PICC and PIV             | Include only the following: CVC Double Lumen, CVC Single Lumen, Peripheral IV, PICC Double Lumen, PICC single lumen, PICC Triple Lumen                                  | Specifies the type of LDAW that was placed   |
| Date of LDAW placement  | XX/XX/XXXX X:XX:XX AM/PM  | The date and time the LDAW was placed  |
| Date of LDAW removal  | XX/XX/XXXX X:XX:XX AM/PM  | The date and time the LDAW was removed   |
| Calculated field:
Duration of LDAW  | Number of hours   | This can be calculated by subtracting the LDAW placement date from the LDAW removal date. Please present results to hours.   |
| LDAW Removal Reason   | Discharge, Catheter damage, therapy complete, leaking, occluded, per order, per protocol, purulent drainage, removed by patient, infiltrated, phlebitis, site change, other (comment) | The reason that the LDAW was removed   |
| Calculated field:
Unit in which the LDAW was placed                                     | Any hospital unit name  | This unit can be determined based on the following criteria: the time of LDAW placement falls between admission into this unit AND before transferred out of or is discharged from this unit.  |

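### Adherence groups 1a and 1b are formed from the same record that holds the complications, and no readable text hides the outcome from the person scoring adherence

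*Combined protocol and SAP*

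**What the plan says.** All references are to the combined protocol and SAP.

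- **Outcome and groups.** Primary Endpoints aims "To document number of mechanical/technical, thrombotic, and other adverse outcomes associated with CVCs, PICCs and HD catheters in two groups". Group 1a is "Clinicians interventions and management in adherence with hospital approved EBP guidelines for CVCs, PICCs and HD catheters" and group 1b is "Clinicians interventions and management not in adherence with hospital approved EBP guidelines for CVCs, PICCs and HD catheters". No threshold or scoring rule is given for either.
- **Source of adherence.** Methodology states that clinician adherence "will be obtained by way of a retrospective medical record review to include data abstraction from nursing and physician notes". The list goes on to consultation, admission and discharge notes, laboratory and diagnostic tests, and flow sheets. It adds that "EPIC, the electronic medical record will be the primary source for the retrospective data collection". Adherence is judged against eight listed policies.
- **Adherence items.** Catheter Management and Care Documented asks for "Number and rate of times that the following best practice indicators were documented". Some items are recorded facts, such as insertion site, unit or syringe size. Others need a comparison with policy or a reading of the charting, such as the access procedure, or saline and heparin flushes given according to policy.
- **Outcome fields.** Catheter Complication lists mechanical, infectious and thrombotic events. Appendix C collects, for each line, a coded field described as "The reason that the LDAW was removed", with values that include occlusion, leakage and purulent drainage. It also has a calculated field for alteplase given while the line was in place.
- **Data flow.** Data Management names the sources as "EPIC and the Business Intelligence Department and review of clinician notes", with entry in REDCap. It does not say which items come from which source.
- **Safeguards.** Confidentiality provides for de-identification at analysis, which protects patients' identity and does not hide the outcome from the abstractor. Limitations mentions incomplete documentation, the single site and the non-experimental design. It does not mention outcome-aware classification.

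**The concern.** In a cohort formed by chart review, the exposure label is itself a measurement. If the person making it may already know that a line occluded or became infected, the error in the label can depend on the outcome. That is differential misclassification, and it can create an association where none exists or distort a real one.

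The likelier mechanism is that a known complication prompts a harder search for a lapse and a stricter reading of borderline charting. This would produce the finding that the study's rationale makes plausible, so it would not look odd in the results. The results are also meant to inform a prospective study.

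The tests in Data Analysis are Pearson correlation and unadjusted group comparisons. They take the 1a/1b label as given and cannot reveal or remove such an error. A masked re-scoring of a subsample could reveal it, but none is planned.

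**Working it through.** **No planning figure to reproduce.** The plan gives 300 records (175 + 75 + 50 = 300) with no alpha, power, effect size or expected 1a/1b split. The calculation below therefore shows sensitivity and does not estimate the bias.

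**Set-up.** There is no true association. The following inputs are assumptions: 40% of lines without a complication are labelled non-adherent, a share *b* of charts is borderline, and borderline charts are called non-adherent with probability *q1* when a complication is known and *q0* = 50% otherwise. The clearly non-adherent share is *c* = 0.40 − 0.50*b*.

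Labelled non-adherent = *c* + *b* × *q*. Odds ratio (OR) = [P1/(1 − P1)] / [P0/(1 − P0)].

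| Case | Complication | No complication | OR |
|---|---|---|---|
| No bias, *q1* = *q0* | 0.40 | 0.40 | 1.00 |
| 1: *b* = 20%, *q1* = 70% | 0.30 + 0.20 × 0.7 = 0.44 | 0.30 + 0.20 × 0.5 = 0.40 | 0.786/0.667 = 1.18 |
| 2: *b* = 40%, *q1* = 80% | 0.20 + 0.40 × 0.8 = 0.52 | 0.20 + 0.40 × 0.5 = 0.40 | 1.083/0.667 = 1.63 |
| Case 1 reversed, *q1* = 50% − 20% = 30% | 0.30 + 0.20 × 0.3 = 0.36 | 0.40 | 0.5625/0.667 = 0.84 |

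**In lines, with 300 records and an assumed 25% complication rate** (75 with, 225 without; 0.40 × 225 = 90 non-adherent among those without):

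- Case 1: 0.44 × 75 = 33. Complications are 33/123 = 26.8% of 1b and 42/177 = 23.7% of 1a. Three labels moved (33 − 30).
- Case 2: 0.52 × 75 = 39. Complications are 39/129 = 30.2% of 1b and 36/171 = 21.1% of 1a. Nine labels moved (39 − 30).

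Under the two-proportion normal approximation with pooled variance and an assumed two-sided 5% level, the chance of a false positive is about 9.5% in case 1 and 44% in case 2, against 5% with no bias.

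**Second parameterisation.** Let *s* be the share of truly adherent lines with a complication that are re-labelled non-adherent, and *a* the true adherent share. Under the null, OR = [1 + *s*·*a*/(1 − *a*)] / (1 − *s*).

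- Cases 1 and 2 are *a* = 60% with *s* = 0.04/0.60 = 6.7% and *s* = 0.12/0.60 = 20%. The formula returns 1.10/0.933 = 1.18 and 1.30/0.80 = 1.63, so the two models agree.
- At *s* = 20%, *a* = 50% gives 1.20/0.80 = 1.50 and *a* = 70% gives 1.467/0.80 = 1.83.
- The complication rate is varied over 14% to 36% (the occlusion range in Background and Significance, which is not a planning assumption) and *a* over 50% to 70%. At *s* = 10% the risk ratio is 1.14 to 1.31 with rejection 9% to 24%. At *s* = 20% it is 1.30 to 1.67 with rejection 22% to 68%.

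If outcome-dependent labelling is removed (*s* = 0), every row returns to a ratio of 1.00 and 5% rejection.

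**The case against.** The strongest reply is that the documents do not show the bias occurring.

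- **One reviewer, one reading.** A reader might infer that a single abstractor reads everything together and so does know the outcome. Methodology lists sources. It does not say who abstracts, in what order, or whether one person scores both. The groups could also be derived at analysis from separately entered items. What stands is that nothing readable prevents outcome-aware scoring.
- **Unreadable text.** Appendix B breaks down at the insertion-attempts field, and only extracts of the policies are reproduced. A safeguard could sit in the lost part, so the absence can be stated only for readable text.
- **Little room for judgement.** Many items are recorded facts, and several visible policy criteria are concrete, such as weekly dressing changes or a 30-second scrub. This narrows the exposure to bias without removing it, because some items do need judgement and no rule turns the items into one label. The borderline shares of 20% and 40% have no source in the documents.
- **Removal reason.** A reader might infer that the notes supply it. In Appendix C it is a coded field, and nothing says that the Business Intelligence Department supplies it. This helps the fix, since a coded field can be withheld and merged later.
- **Direction.** Lines with complications may attract fuller charting, so that more practices appear documented and the association moves the other way. This is fair, and masking the abstractor would not cure that effect.
- **Exploratory aim.** The primary objective is exploratory and Limitations already restrains correlational inference. That lowers the stakes, but it does not justify leaving open a gap that is cheap to close before abstraction and cannot be undone afterwards.

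**Conclusion.** The concern holds as a gap in procedure. Adherence, which defines the primary comparison groups, comes from the record in which complications are noted, and no readable passage masks the outcome or orders the two steps. The outcome may be known when judgement items are scored, and the planned unadjusted tests cannot remove the resulting bias.

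Its size is unknown. The illustrative OR under no true association runs from 1.00 to about 1.6 in the worked cases. It reaches 1.83 if 20% of adherent lines with complications are re-labelled and the adherent share is 70%, and falls to 0.84 if case 1 is reversed. These figures rest on assumed borderline shares, calling probabilities and adherent share; the false-positive rates also assume a complication rate and a 5% level.

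A reader might go further and conclude that the association will be inflated, or that a positive result would be an artefact. The documents support neither: they establish the opportunity for bias, with a plausible but uncertain direction.

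**What to change.** Change Methodology and the REDCap set-up before abstraction starts.

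1. Fix in writing, before review, the rule that turns the items under Catheter Insertion and Catheter Management and Care Documented into 1a or 1b. Derive the label from the items and not from a global judgement.
2. Score those items first, starting with the insertion record, flow sheets and routine nursing and physician care notes. Keep the complication, removal-reason and alteplase fields out of view. Then lock the items.
3. After the lock, open the complication form and merge removal reason and alteplase use by line.
4. Keep every source named in Methodology. Read consultation and discharge notes after the lock, and allow an adherence item charted only there to be added with an audit-trail flag. Barring these notes would create missing adherence data.
5. Record when the abstractor met outcome information before the lock. Repeat the primary comparison without post-lock changes and without the unmasked lines.
6. Add outcome-aware classification to Limitations.

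The cost is a form-order and lock setting, a short addition to the text, and some charts opened twice. No new data or staff are needed. Masking stays partial: care notes and flow sheets may reveal the event, the readable Appendix B form covers placement and removal together, and one listed item, the infusion pump pressure alarm, may itself hint at occlusion.

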## **DATA COLLECTION TOOL**

The data collection tool is systematically organized to facilitate retrieval of data from the electronic medical record. See Appendix B. The data collection tool includes specified items, values, and descriptions. See Appendix C.

## **STUDY PERIOD**

The one year retrospective study will be implemented immediately after institutional review board approval.

## **INCLUSION CRITERIA**

Adult patients in MICU, CCU, CSICU, SICU and hemodialysis with either CVCs, PICCs, or HD catheters.

## **CASCADE STUDY**

13

Version 1.1 09/27/2017

## **EXCLUSION CRITERIA**

Pediatric (including neonates), obstetric and gynecology, medical-surgical, and oncology patients.

## **SAMPLE SIZE**

The total number of CVCs and PICCs inserted in MICU, CCU, CSICU, SICU in year 2015 and 2016 is summarized in Table 2 and Table 3 below:

**Table 2 – CVCs Inserted in Critical Care Units**

| CVC | 2015 | 2016 |
|------------|-------------|-------------|
| MICU       | 132         | 176         |
| CCU        | 168         | 160         |
| CSICU      | 164         | 80          |
| SICU       | 204         | 192         |

**Table 3- PICCs Inserted in Critical Care Units**

| PICC | 2015 | 2016 |
|-------------|-------------|-------------|
| MICU        | 32          | 10          |
| CCU         | 60          | 32          |
| CSICU       | 56          | 68          |
| SICU        | 44          | 56          |

A convenience sample of three-hundred medical records will be reviewed for this study, one-hundred and seventy-five CVCs, seventy-five PICCs, and fifty HD catheters representing 25%, 45% and 10% respectively of the total number of catheters inserted in 2016.

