## **LIMITATIONS**

A limitation in use of retrospective data collection from the patients medical record is incomplete and/or missing data related to variability in the quality and completeness of documentation by healthcare team members. In addition, because this is a single site study, the generalizability of the study's findings will be limited to the medical center. Also, the non-experimental design limits correlation between adherence to the guidelines and catheter success rate.

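### The 300 charts are chosen by convenience although adherence and complications are both already on record, so chart choice may bias the primary association and the practice rates

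*Combined protocol and SAP*

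**What the plan says.** The sampling statement stands under Table 3 in the Sample Size section: "A convenience sample of three-hundred medical records will be reviewed for this study, one-hundred and seventy-five CVCs, seventy-five PICCs, and fifty HD catheters", described as "representing 25%, 45% and 10% respectively of the total number of catheters inserted in 2016". Nothing else in the document says how a chart is picked. There is no random, consecutive or systematic rule, no allocation by unit, and no masking of the person choosing.

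Tables 2 and 3 are introduced as "The total number of CVCs and PICCs inserted in MICU, CCU, CSICU, SICU in year 2015 and 2016". HD catheters are not tabulated. Data Management says: "All data in this study will be obtained from multiple sources: EPIC and the Business Intelligence Department and review of clinician notes". Appendix C asks for one row per item, with the medical record number, placement and removal times, and the unit of placement.

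The Primary Objective is to explore the association between adherence and complications, and Data Analysis offers only unadjusted comparisons. Limitations names "incomplete and/or missing data related to variability in the quality and completeness of documentation by healthcare team members", the single site and the non-experimental design, but not the way charts are selected.

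**The concern.** In a chart review the exposure and the outcome both exist before the chart is chosen, so a convenience choice can depend on either or both. Two features make this more than a generic worry.

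- **Adherence is measured through documentation.** The list headed Catheter Management and Care Documented counts how often each practice indicator was recorded. Preferring complete charts, which are easier to abstract, comes close to selecting on the exposure.
- **Complications are easy to find.** Appendix C extracts the removal reason (occluded, leaking and so on) and any alteplase use while the line was in place.

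Two things are at stake. The first is the primary association. The second is the description of practice variation, which is the aim under Study Purpose and Rationale and the subject of the Secondary Endpoints. The results are meant to shape a later prospective study.

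**Working it through.** **Inputs.** Sample: 175 CVC, 75 PICC, 50 HD. Table 2, 2016 (MICU, CCU, CSICU, SICU): 176, 160, 80, 192. Table 3, 2016: 10, 32, 68, 56. The plan gives no alpha, power, adherence rate or complication rate for the sample size, so those used below are assumptions.

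**The plan's own figures**
- 175 + 75 + 50 = 300. Reproduced.
- PICC: 10 + 32 + 68 + 56 = 166; 75/166 = 45.2%. The stated 45% is reproduced.
- CVC: 176 + 160 + 80 + 192 = 608; 175/608 = 28.8%. The stated 25% is not reproduced (25% of 608 is 152). It should be reconciled, but the present point does not depend on it.
- HD: 10% implies 50/0.10 = 500 catheters. There is no table to check this against.

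**Effect on the odds ratio.** Let s be the probability that a chart is picked, with A adherent, N non-adherent, 1 complication, 0 none. For non-adherent versus adherent:

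observed OR = true OR × F, where F = (sN1 × sA0)/(sN0 × sA1)

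| Assumed sA0, sA1, sN0, sN1 | F | 1/F (adherent versus non-adherent) |
|---|---|---|
| 0.30, 0.40, 0.15, 0.20 | 0.06/0.06 = 1.0 | 1.0 |
| 0.30, 0.40, 0.25, 0.40 | 0.12/0.10 = 1.2 | 0.83 |
| 0.30, 0.40, 0.15, 0.40 | 0.12/0.06 = 2.0 | 0.50 |
| sN1 twice a common s | 2.0 | 0.50 |
| sN1 half a common s | 0.5 | 2.0 |

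In the first row both influences operate but multiply: a complication raises the chance of selection by 4/3 in each group, and the odds ratio is untouched. In the last row a true odds ratio of 2 would appear as 2 × 0.5 = 1.0.

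How often could this mislead? Assume no true association, 250 CVC and PICC charts, a two-sided 5% test (normal approximation), adherence of 30–70% and complication rates of 14–36%. That last range is borrowed from the occlusion figure in Background and Significance and is not a design input. If sN1 is 1.5, 2 or 3 times the common s, the chance of p < 0.05 is about 17–34%, 43–76% or 86–99%.

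**Effect on rates.** Assume 50% true adherence and 20% complications in both groups, with the first row of the table:
- adherent charts picked: 0.5 × (0.8 × 0.30 + 0.2 × 0.40) = 0.16
- non-adherent charts picked: 0.5 × (0.8 × 0.15 + 0.2 × 0.20) = 0.08
- observed adherence: 0.16/0.24 = 66.7%, against 50%
- observed complications: 0.5 × 0.2 × (0.40 + 0.20)/0.24 = 25%, against 20%

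Selection on documentation alone (0.30 for adherent, 0.15 for non-adherent) also gives 0.15/(0.15 + 0.075) = 66.7%.

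**Unit mix.** Quotas are set by catheter type only. MICU (176) or SICU (192) could each supply all 175 CVCs. That is an arithmetic extreme, but nothing in the plan prevents it. Allocation in proportion to the 2016 totals:
- CVC, 175 × unit/608: 50.7, 46.1, 23.0, 55.3, rounded to 51, 46, 23, 55 (sum 175)
- PICC, 75 × unit/166: 4.5, 14.5, 30.7, 25.3, rounded to 5, 14, 31, 25 (sum 75; the unrounded 4.52 and 14.46 settle the first two)

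**Pooling across types.** If the implied 500 HD catheters is right, HD makes up 500/(608 + 166 + 500) = 39% of catheters but 50/300 = 17% of the sample.

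**The case against.** The strongest reply is that no bias has been shown. Influences on selection that act independently and multiply leave the odds ratio intact, and so does selection on adherence alone or on complications alone. Every selection probability above is assumed. The study is exploratory, and Limitations already concedes that its design restricts what can be said about adherence and catheter success. All of this stands. It limits the claim to a risk, but it does not supply a selection rule, and it does not protect the descriptive rates, which shift even when F = 1.

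A reader might also infer from Tables 2 and 3 that every eligible catheter is already listed and that only a draw is missing. The documents do not support that:
- The tables are counts by unit, not records, and are not shown net of the Exclusion Criteria.
- They cover insertions in four ICUs, whereas the Inclusion Criteria cover patients in those units plus hemodialysis. The operating room and interventional radiology also appear as places of insertion.
- Study Period does not fix 2016 as the record year.
- The line types in Appendix C include no HD catheter and no triple-lumen CVC.

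What the documents do show is that a list can be built, because Appendix C already specifies the fields that a unit-stratified list needs.

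**Conclusion.** The point holds as a design weakness that is cheap to correct. Convenience selection, with both variables visible and no rule stated, may create or hide the primary association. The size depends wholly on assumed selection probabilities. In the cases shown, the odds ratio (non-adherent versus adherent) is multiplied by anything from 0.5 to 3, including 1.0. Distortion of the documented-practice rates needs less: selection on documentation quality is enough.

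Two stronger conclusions are not supported. Convenience selection does not necessarily bias the odds ratio. Nor would a random draw at 175, 75 and 50 by itself make pooled rates representative of the hospital, because the sampling fractions differ: 28.8% of CVCs, 45.2% of PICCs and a stated 10% of HD catheters. Confounding, and the measurement of adherence through documentation, would remain under any sampling scheme.

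**What to change.** In the Sample Size section, replace the convenience sample with a computer-generated random sample of the same 175 CVCs, 75 PICCs and 50 HD catheters, drawn before abstraction from an EPIC/Business Intelligence list of insertions in a stated year.

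- Allocate CVCs and PICCs in proportion to unit. On the 2016 totals this is MICU 51, CCU 46, CSICU 23, SICU 55 for CVCs, and 5, 14, 31, 25 in the same order for PICCs. Recalculate once the exclusions have been applied to the list.
- Widen the Appendix C extract to HD catheters and triple-lumen CVCs, and build the HD list before drawing from it.
- Replace an ineligible record with the next on the random list, and report how many were replaced and why.
- Report rates by catheter type, or weight pooled rates by the inverse of the sampling fraction.

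No charts are added. The cost is the work of building the list and slower abstraction of charts that are poorly documented.

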## **PRIMARY OBJECTIVE**

1. To explore the association between mechanical/technical, thrombotic, and other adverse outcomes associated with CVCs, PICCs and HD catheters due to variation in insertion and management practices and with adherence to hospital approved EBP guidelines for CVCs, PICCs and HD catheters.

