## **DATA ANALYSIS**

The summary of the demographic characteristics will be presented. Continuous variables will be summarized using mean (SD) or median (interquartile range) depending on whether or not the data follow the normal distribution. Categorical variables will be summarized by frequency (percentage). Correlational analysis will be performed utilizing Pearson Correlation. Comparison of continuous variables between any independent groups will be examined using two-sided T-test or two-sided Wilcoxon rank sum test, analysis of variance (ANOVA) or Kruskal-Wallis test followed by pairwise tests, as appropriate. Categorical variables will be

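### The primary adherence–complication comparison spans three catheter types with no stratified or adjusted test planned; as a minor point, the 25% CVC share disagrees with Table 2

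*Combined protocol and SAP*

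**What the plan says.** The Primary Objective is "To explore the association between mechanical/technical, thrombotic, and other adverse outcomes associated with CVCs, PICCs and HD catheters" and adherence to the hospital's guidelines. Primary Endpoints then asks for the number of mechanical, thrombotic and "other adverse outcomes associated with CVCs, PICCs and HD catheters in two groups", one adherent and one not. All three catheter types appear together in both places.

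Sample Size sets the numbers per type: "A convenience sample of three-hundred medical records will be reviewed for this study", made up of "one-hundred and seventy-five CVCs, seventy-five PICCs, and fifty HD catheters representing 25%, 45% and 10% respectively" of the 2016 total. The supporting tables cover "The total number of CVCs and PICCs inserted in MICU, CCU, CSICU, SICU in year 2015 and 2016". Inclusion Criteria is wider: "Adult patients in MICU, CCU, CSICU, SICU and hemodialysis with either CVCs, PICCs, or HD catheters".

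For continuous variables, Data Analysis says: "Comparison of continuous variables between any independent groups will be examined using two-sided T-test or two-sided Wilcoxon rank sum test", with ANOVA or Kruskal-Wallis as further options. Categorical variables get Fisher's exact or Pearson's chi-square test, and there is an unspecified Pearson correlation. No test is tied to the adherence comparison, and none has strata or covariates.

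**The concern.** The mix of catheter types is set by the sampling (175/75/50), not by how the lines occur in the hospital. The protocol itself treats the types as different. Table 1 and the Background give them different sites, uses and dwell times, and Methodology lists separate policies for CVCs, PICCs and dialysis catheters. So adherence and complication risk may both vary by type. If they do, a single two-by-two table over 300 lines can show an association that comes only from type, or hide a real one. The results are meant to inform a prospective study, so a misleading association would carry forward.

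The quoted percentages raise a smaller matter. They are the plan's only description of how the sample relates to the available catheters, and one of them does not agree with the plan's own table.

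**Working it through.** **Sampling shares.** Share = sampled number / 2016 total over the four units.

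- PICC (Table 3): 10 + 32 + 68 + 56 = 166, and 75/166 = 45.2%. This reproduces the stated 45%.
- CVC (Table 2): 176 + 160 + 80 + 192 = 608, and 175/608 = 28.8%. The stated 25% is not reproduced; 25% of 608 is 152. Rounding to 25% needs a total of 687 to 714, which is 79 to 106 more than the table shows.
- Other CVC denominators: 668 (2015) gives 26.2%; 638 (two-year mean) gives 27.4%; 1,276 (both years) gives 13.7%; 774 (CVC plus PICC, 2016) gives 22.6%; dropping any one unit from 2016 gives 33.1% to 42.1%. None gives 25%.
- HD: 10% implies 477 to 526 catheters. No HD count is given, so this cannot be checked.

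**Confounding by type.** The numbers per type, n = 175/75/50, come from Sample Size. Adherence a and complication risk p by type are assumptions, because the documents give neither. Within each type, p is the same for adherent and non-adherent lines, so there is no true effect.

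Crude adherent rate = Σ n·a·p / Σ n·a. Crude non-adherent rate = Σ n·(1−a)·p / Σ n·(1−a).

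First strong case, a = 80/70/50%, p = 10/15/30% (CVC/PICC/HD):
- adherent: (14 + 7.875 + 7.5)/(140 + 52.5 + 25) = 29.375/217.5 = 13.5%
- non-adherent: (3.5 + 3.375 + 7.5)/(35 + 22.5 + 25) = 14.375/82.5 = 17.4%
- risk ratio 17.4/13.5 = 1.29

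Second strong case, a = 50/70/80%, same p:
- adherent: 28.625/180 = 15.9%
- non-adherent: 15.125/120 = 12.6%
- risk ratio 0.79

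Simulated rejection with no adherence effect (20,000 studies per row, two-sided 5% level assumed because the plan states none; uncorrected chi-square):

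| Adherence, CVC/PICC/HD | Complications | Crude chi-square |
|---|---|---|
| 80/70/50% | 10/15/30% | 14.9% |
| 50/70/80% | 10/15/30% | 12.2% |
| 75/70/65% | 10/15/30% | 6.3% |
| 65/70/75% | 10/15/30% | 5.6% |
| 80/70/50% | 10/12/15% | 6.3% |
| 50/70/80% | 10/12/15% | 5.4% |
| 70/70/70% | 10/15/30% | 4.9% |

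The Cochran-Mantel-Haenszel test stratified by type rejects in about 5% throughout (4.9% and 5.2% in the two strong cases). Fisher's exact test gives 12.6% and 10.7% in those two cases.

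With a true odds ratio of 2 for non-adherence and the complication rates 10/15/30% taken as the risk in adherent lines:

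| Adherence | Crude chi-square | Stratified |
|---|---|---|
| 80/70/50% | 85% | 55% |
| 50/70/80% | 27% | 57% |
| 70/70/70% | 56% | 57% |

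The 85% is not a gain in power: confounding pushes in the same direction as the effect and inflates the crude result. In the second row it pushes the other way. The last row shows that stratifying costs nothing here when there is no confounding.

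**The case against.** The study is exploratory and correlational, and Limitations already says that the design restricts what can be concluded about adherence and catheter success. The general wording on independent groups would allow the tests to be run within each type, and nothing commits the analyst to pooling. The strong cases combine a threefold gradient in complications with a 30-point gradient in adherence, and no figure in the documents supports either. Milder gradients bring the crude test close to its nominal level. Catheter type is also not the only possible confounder: unit and dwell time are collected too.

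Most of this stands and limits the weight of the point. It does not remove it. Permission to compare groups is not a plan to control for type, and Limitations does not mention type. The Hypothesis section also frames a significance statement, so the choice of test matters. Stratifying by type leaves other confounders in place, but type is the factor on which the sample was built.

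A further objection is that the endpoint is worded as a number of outcomes, so a method for yes/no data may not fit. That is right, and the fix has to cover both forms. The plan also gives no rule that labels a line's care adherent or not; a crude test needs such a rule as much as a stratified one.

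On the percentage, Sample Size does not name its denominator, and Inclusion Criteria reaches beyond the four units, so a CVC total near 700 is possible. The PICC match to the four-unit total weakens that reading but does not exclude it.

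**Conclusion.** The point holds as a gap in the analysis plan. For the primary association, only unadjusted tests are named across three types sampled in fixed numbers. If the types are pooled, bias arises when adherence and complication rates both differ by type; it is zero if either is equal across types. Under the assumed rates, crude false rejection runs from about 5% to 7% (mild gradients) to 12% to 15% (strong gradients), against about 5% when stratified. With an odds ratio of 2 and strong gradients, the crude test rejects in 27% or 85% of studies, depending on the direction of confounding, against 55% to 57% stratified.

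Three stronger readings are tempting and are not supported:
- that the plan commits to a pooled test: Primary Endpoints does not say so;
- that the primary result will be biased by a known amount or in a known direction: no rates by type are given;
- that the percentage mismatch undermines the sample of 300: it changes neither that number nor any analysis, and it may reflect an unstated denominator.

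The convenience selection of charts and the line types listed in the data collection tool are separate questions, and this conclusion does not depend on them.

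**What to change.** In Data Analysis, state that complications will be reported by adherence within each catheter type, with 95% confidence intervals, and that the association will be tested with catheter type as a stratum or covariate. State which form the endpoint takes:

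- any complication per line (yes/no): Cochran-Mantel-Haenszel test with a common odds ratio and its 95% confidence interval, or logistic regression on adherence and catheter type;
- a count per line: Poisson or negative binomial regression on adherence and catheter type.

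In Sample Size, change 25% to 28.8% and keep 175 CVCs, or name the wider denominator used. Give the 2016 HD total behind the 10%.

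The cost is a few sentences and no extra charts. The drawback is imprecision by type. With half-width 1.96·√(p(1−p)/n) and assumed overall complication rates, the 95% half-widths are about 4.4 points for CVCs (10% of 175), 8.1 for PICCs (15% of 75) and 12.7 for HD catheters (30% of 50). They will be wider once each type is split by adherence. The by-type figures should therefore be read as description, with the stratified or adjusted estimate as the main result.
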